Our long-term objective is to evaluate the efficacy of curcumin (CC) in preventing a recurrence of chronic subdural hematoma (cSDH) following surgical evacuation. Recurrence is defined as an increase in total hematoma volume on the operated side compared to a post-operative day one CT scan with persistent or recurrent neurological symptoms. We propose this pilot study to assess feasibility and obtain preliminary benefit assessment of the proposed therapeutic approach.

Objective 1: To determine if the use of CC treatment reduces the total hematoma cavity volume over a 6-month interval, compared to a post-subdural drain removal CT scan. This evaluation is expected to offer sufficient evidence for a larger definitive trial.

Objective 2: Study the effect of CC on interleukin-8 (IL-8)-induced disruption of endothelial permeability *in vitro* using human vascular endothelial cells.

Central hypothesis: CC treatment prevents the re-accumulation of cSDH, which may occur by inhibition of IL-8 and allowing resolution of the total hematoma cavity volume over six months.

2. Background

Chronic subdural hematomas (cSDH) are extra-axial fluid collections in the cranium that can result in brain compression and neurological decline. cSDH commonly occurs after traumatic brain injury (TBI); though, many times there is no history of trauma. The incidence of cSDH is expected to significantly rise, due to an increasing elderly population worldwide. This is a common and challenging neurosurgical problem due to their ability to recur requiring repeated surgical re-evacuation. Repeat surgery comes with additional morbidity as well as rising costs for both patients and hospitals. The literature reported recurrence rates ranging from 2.3% to 33%.^{8,29,32,40}

We recently completed a retrospective review of 147 chronic unilateral, subdural hematomas and 75 chronic bilateral subdural hematomas at our institution from 2007-2014 (IRB#14-160). The data show that 15.65% of the unilateral group and 9.33% of the bilateral group showed recurrence.¹⁷ Operative decompression is the treatment of choice; however, an effective therapy preventing recurrence of cSDH after surgical intervention has not yet been found. Our long-term goal is to develop a therapeutic approach focused on the prevention of cSDH recurrence after initial surgical intervention.

cSDH is characterized by encapsulation of the subdural hematoma within newly developed membranes mostly associated with aberrant neomembrane neovascularization through inflammatory processes. Current research efforts have been targeted at investigating the composition of cSDH fluid. Angiogenesis growth factors, inflammatory cytokines and matrix metalloproteinases (MMP) are believed to play a critical role in increased microvascular leakage and hemorrhage.³⁸ We previously showed that samples of subdural hematoma fluid (SDHF) from cSDH patients contained several molecules significantly upregulated compared to venous blood. These included stromal-derived growth factor-1 (SDF-1), vascular endothelial growth factor (VEGF), and metalloproteinase MMP-9. These results led to our search for the upstream regulators of these molecules that could be targets for cSDH therapy.

We found that the pro-angiogenic and pro-inflammatory cytokine **interleukin-8** (IL-8/CXCL8) was elevated by more than 300 times in SDHF but restricted to SDH, not systemically.^{38,39} Frati et al. reported that increased levels of the inflammatory cytokines IL-6 and IL-8 were correlated with cSDH and possible key stimulators of inflammation and hemorrhage during cSDH progression.⁷

IL-8 is implicated in a wide variety of clinical disorders, including cancer, amyotrophic lateral sclerosis (ALS), multiple sclerosis (MS), and cystic fibrosis, which prompted an intensive search for neutralizers and inhibitors of this cytokine. Numerous investigations have identified curcumin as a

potent inhibitor of IL-8.^{1,3,14} **Curcumin**, a polyphenolic compound derived from the dietary spice turmeric, possesses diverse pharmacologic effects, including anti-inflammatory, antioxidant, antiproliferative and antiangiogenic activities. Various animal models and human studies proved that curcumin is extremely safe, even at very high doses.¹¹ Numerous research investigations identified the compound curcumin as a potent inhibitor of IL-8 production and signaling.¹⁰ Thus, this could be regarded as a safe over-the counter remedy for targeting IL-8-initiated pathological conditions.⁵

“Some promising effects have been observed in patients with various pro-inflammatory diseases including cancer, cardiovascular disease, arthritis, uveitis, ulcerative proctitis, Crohn’s disease, ulcerative colitis, irritable bowel disease, tropical pancreatitis, peptic ulcer, gastric ulcer, idiopathic orbital inflammatory pseudotumor, oral lichen planus, gastric inflammation, vitiligo, psoriasis, acute coronary syndrome, atherosclerosis, diabetes, diabetic nephropathy, diabetic microangiopathy, lupus nephritis, renal conditions, acquired immunodeficiency syndrome, β -thalassemia, biliary dyskinesia, Dejerine-Sottas disease, cholecystitis, and chronic bacterial prostatitis.”¹⁰ It has also been found to directly inhibit the production of the pro-inflammatory, and pro-angiogenic chemokine IL-8 (CXCL8), Vascular Endothelial Growth Factor (VEGF), and basic Fibroblast Growth Factor (bFGF). This discovery has led to additional research in the oncology field for potential clinical uses of this herb. With the current literature indicating the role of IL-8 in subdural hematoma expansion, our hope is to evaluate the role of curcumin in the prevention of cSDH expansion and recurrence.

Inflammatory Markers

Suzuki et al. and Stanisic et al. conducted independent studies investigating inflammatory markers found locally at the site of chronic subdural hematomas, as well as systemically through the peripheral venous blood. Both groups’ papers concluded that the concentration of inflammatory markers is significantly elevated within the subdural hematoma cavity when compared to peripheral blood samples.^{38,39} Suzuki et. al. measured IL-6 and IL-8 to be 10-times higher in the fluid of chronic subdural hematomas compared to subdural effusion patients.¹

Stanisic et al. also investigated the concentration of both pro-inflammatory and anti-inflammatory cytokines in the chronic subdural hematoma fluid compared to the systemic circulation. The objective of his study was to demonstrate that not only are pro-inflammatory markers (IL-2R, IL-6, IL-7) elevated within the subdural fluid but that the ratio of pro-inflammatory to anti-inflammatory markers (IL-10, IL-13) is elevated within this subdural hematoma fluid as well. They concluded that there is a poorly coordinated innate immune response within the chronic subdural hematoma cavity, which leads to an abnormally increased inflammatory response. This ultimately leads to the formation and progression of chronic subdural hematomas.³⁸

Frati et al. evaluated whether local inflammation within the subdural hematoma cavity was a risk factor for the recurrence of posttraumatic chronic subdural hematomas. Although the authors were more interested in measuring the inflammatory markers locally within the hematoma site; their conclusion that high levels of inflammatory cytokines (IL-6 and IL-8) were statistically correlated with recurrence of the hematoma is extremely relevant to our area of interest.⁷

A South Korean study chose to investigate the components of both the chronic subdural hematoma fluid as well as their outer membrane in 66 patients that underwent burr-hole hematoma drainage. They found a statistically significantly increase in the concentration of IL-6 within the hematoma fluid of patients that had a recurrence. In addition, they found a significantly stronger immune-histochemical staining of VEGF and bFGF within the outer membrane of hematomas that recurred compared to the non-recurrence group. This study demonstrated that IL-6 within the hematoma fluid and VEGF and bFGF in the outer membrane are direct risk factors for the recurrence of cSDH.¹⁵

Hidaka et al. conducted a study looking at CC effects on the production of IL-8, and ultimately, its impact on NF-kappaB activation and human pancreatic carcinoma cell growth. The authors found

that the production of IL-8 was inhibited by curcumin in a dose dependent manner. Additionally, it was found that CC inhibited IL-8 induced receptor internalization as well. These two findings were significant for the author's investigation into tumor cell growth. More relevant to our interest, it demonstrated that CC inhibits the inflammatory response of IL-8 through a decrease in its production and an inhibition of IL-8 induced receptor internalization.¹⁴

It should first be noted that IL-8 is a known angiogenic factor, and the previous papers mentioned above showed increased IL-8 within the cavity of chronic subdural hematomas.^{7,38,39} CC has also been found to have anti-angiogenic properties as well. By proving curcumin's inhibitory effect on IL-8, current research has already suggested that CC is an anti-angiogenic molecule. Three additional papers investigated this anti-angiogenic activity directly. Bhandarkar et al. found that CC directly down regulates the activity of both VEGF as well as bFGF, while also inhibiting multiple signal transduction pathways that are involved in angiogenesis.³ Another study, conducted in Boston by Arbiser et al. also found that CC significantly inhibited bFGF-mediated corneal neovascularization in mouse models.¹ The molecular mechanisms of curcumin's anti-angiogenic effects were investigated by Gururaj et al. who found CC to have a direct time-dependent and dose-dependent inhibition of VEGF at the level of gene expression. In their study; however, CC was directly injected into the intra-peritoneal cavity of mice. This was not only found to not be cytotoxic, but it also reduced ascites by 66% in mice with Ehrlich ascites tumor cells. Though this is just an initial mouse model, it may be one step closer towards understanding the non-cytotoxic effects of CC for future research.

Brain Injury

CC has demonstrated promising results in multiple studies related to brain injury including intraparenchymal hemorrhage, acute stroke, subarachnoid hemorrhage, and general injury to the blood-brain-barrier.^{16,20} 6 hours following intracerebral hemorrhage in adult mice, curcumin was administered in clinically relevant doses of 75-300 mg/kg. After 72 hours, there was a reduction in hematoma size, decreased vasogenic edema secondary to a less damaged blood-brain-barrier, decreased inflammatory markers, and overall improved neurological outcome.¹⁶ After discussing the role of T-lymphocytes in contributing inflammation and worsening neuronal injury, mouse models were used to demonstrate a suppression of T-lymphocyte infiltration in the brain after administration of curcumin. There was also a reduction in cerebral edema and improvement of neurological scores.²⁰ One study administered low dose (80mg/day) curcumin to healthy middle-aged adults (40-60 years of age), when compared to a placebo group. The CC group had lower levels of plasma triglyceride, salivary amylase levels, plasma beta amyloid protein concentrations (protein responsible for Alzheimer's disease and other forms of intracerebral hemorrhage), and other beneficial health effects.⁵

Alzheimer's Trial

Several studies evaluating the possible protective properties of CC in Alzheimer's disease have been published.³⁰ CC, commonly found in Indian spices, is hypothesized to be part of the low incidence of Alzheimer's disease in Indians. A study published by DiSilvestro et al. demonstrated that **80 mg of CC daily** decreased the plasma levels of beta-amyloid, the main component in the amyloid plaque found on histopathology of Alzheimer patients.⁵ Currently, a phase II study (NCT01001637), using positive results from animal models, is following Alzheimer's patients for 6 months, with either a **2,000-3,000mg BID dose of curcumin** versus the placebo. Animal models have already demonstrated significantly reduced memory deficit with curcumin administration.^{13,21} Much of their current research is at targeting a formulary form of CC that can cross the blood brain barrier. Fortunately, in our population of patients with chronic subdural hematomas, we assume that their blood brain barrier is leaky from the presence of inflammatory markers that contribute to the recurrence of the hematoma. Our capsule contains 270 mg of pure curcuminoids (curcumin) and 3mg of black pepper extract. The recommended serving size is 3 capsules a day. Therefore, the patients will receive **810mg of pure curcumin** and 9mg of black pepper extract (pepperine) per day.

Curcumin with Piperine

It was recently detected that combining CC with piperine (black pepper extract, also known as pepperine or BioPerine), a known inhibitor of hepatic and intestinal glucuronidation, enhances the serum concentration, extent of absorption and bioavailability of CC in both rats and humans.³⁵ Srinivasan wrote an exhaustive review of the physiological effects of piperine and found that previous reported concerns were based on questionable reports, and it is in fact safe for human consumption.³⁶ Myers et al demonstrated that gastric bleeding was no different than that from aspirin, and this was in higher doses of pepper consumption.²⁵ Therefore, CC supplement is now used in combination with the black pepper extract (Appendix 1).

Black pepper/piperine is listed under the FDA as being safe (Appendix 2).²³ The average amount of pepper consumed by a person during a day in the United States is 359 mg, which translates to 18-32 mg of piperine a day. Furthermore, rat trials show a daily intake of 5 to 20 times the average daily dose of humans produced no clinical symptoms. Furthermore, studies on acute, subacute, and chronic piperine toxicity show no abnormalities or clinical symptomatology, or significant blood chemistry data in laboratory animals. Black pepper extract has a high degree of safety being used nutritionally. The amount of piperine that is formulated in the curcumin capsules is several thousand times less than the LD₅₀ established in mice and rats.²² Our capsule contains 270 mg of pure curcuminoids (curcumin) and 3mg of black pepper extract. The recommended serving size is 3 capsules a day. Therefore, the patients will receive 810mg of pure curcumin and **9mg of black pepper extract** (pepperine) per day, which is less than the average amount of pepper consumed by a person daily in the United States.

CT Scans

The use of CT scans to evaluate the volume of hemorrhage in cSDH patients is the standard of care. At our institution, it is standard practice to obtain a minimum of three CT scans over the course of surgical management of a cSDH. The **first CT scan** is obtained pre-operatively to characterize the subdural and determine subsequent management. In patients who receive surgical evacuation, a **post-operative scan (second scan)** is performed to demonstrate adequate drainage of the fluid, improvement in midline shift, and to assess for new hemorrhages or strokes. If a subdural drain is placed intra-operatively, a **third scan** is obtained within 24-hours of subdural drain removal. One study on acute subdural hematomas (aSDH) reported an average of 4.3 CT studies per patient during their hospital stay.³⁴ There is extensive empirical evidence that strongly supports the correlation between pre-operative imaging and pre-and post-operative neurological data and the risk of rebleeding regardless of drain placement and removal.^{12,26,27,33,41} Most researchers agree that the drain removal procedure is risky, but there is no clear consensus on what exactly defines this risk; therefore, a post-operative scan is felt to be advantageous to document the formation of new hemorrhage, hemorrhage as fragile brain tissue and vasculature may be disturbed.^{4,33}

In a study by Stanisic et al. evaluating the use of CT imaging to predict postoperative recurrence of cSDH, the authors determined three predictors of recurrence: **preoperative volume of the hematoma**, CT density, and **residual total hematoma cavity volume** (fluid and pneumocephalus) based on post-subdural drain removal CT scan.³⁷ This group performed a pre-operative CT scan (**scan one**), a post-operative scan within 24 hours of surgery following drain removal (**scan two/three**), and **monthly interval** scans until complete disappearance of the fluid collection, for up to 7 months. **Relapse** was defined as increased total hematoma cavity volume on the operated side compared to a post-operative day 1 CT scan, with persistent or recurrent neurological symptoms. This group found that in patients with a pre-operative hematoma volume of less than **115cc**, the probability of no recurrence was 94.4%. In patients with a post-operative subdural drain removal scan that demonstrated a residual total hematoma cavity volume of less than **80cc**, the probability of no recurrence was 97.4%.

Title: Clinical Action of Curcumin/Turmeric In chronic Subdural hematoma recurrence (CACTIS)

Interestingly, the group also found that in the patients who had complete disappearance of the residual cSDH, this could be seen by **120 days (4 months)**.

In another study evaluating 986 cSDH cases status post evacuation, their protocol included repeat CT scans 6 and 12 weeks after discharge to evaluate for residual hematoma.³¹ They defined recurrence of the cSDH, if the hematoma cavity volume increased within three months of surgery but no specific measurements were provided. All patients in this study were followed for three months following surgery. The **Markwalder grading score** (MGS) was used as a measure of patient's neurological status.

Lin et al. published an article on utilizing hematoma density to assess post-operative recurrence in cSDH patients.¹⁹ In these patients, CT scans were completed 24 hours following surgery, similar to our institution, and on monthly intervals for up to 6 months and only discontinued if complete disappearance of subdural collection was observed.

Utilizing Stanisic et.al findings, our protocol will only include patients with a pre-operative hematoma volume of **115cc** or greater. Similar to this group, we will perform monthly interval CT scans until the total hematoma volume is measured to be less than **80cc**³⁷ our working definition of resolution. At this point, we will determine that the patient has met criteria for **resolution** of the cSDH and would not require further imaging. If the patient demonstrates a neurological change or increased volume, an earlier CT scan will be performed, regardless of volume size.

Conclusion

The current literature and our own preliminary data have demonstrated that there is local elevation of pro-inflammatory chemokines and pro-angiogenic factors within the subdural hematoma cavity of chronic subdural hematomas that are not found systemically. CXCL8 (IL-8) demonstrates both pro-inflammatory and pro-angiogenic properties. Curcumin has shown to directly inhibit the production and activity of CXCL8 (IL-8) *in vitro* and *in vivo*, as well as down regulating the activity of VEGF and bFGF. These combined effects make CC an important anti-inflammatory and anti-angiogenic molecule that has the potential to reduce the recurrence rate of chronic subdural hematomas. We expect that CC will prevent/reduce persistent hemorrhage within the subdural hematoma cavity, by blocking IL-8-induced disruption of the blood vessels. Specifically, CC is expected to preserve blood vessel leakage and accumulation of blood in SDH cavity, by blocking destructive effect of IL-8 on the vascular endothelial tight junctions.

3. Study Design

This is a *double-blinded, randomized placebo-controlled pilot study*. The patients, neurosurgeons, nurses and clinical coordinators will be blinded except for the research pharmacists who will keep a key linking a code # on a bottle handed to the clinical coordinator and the patient's MRN #. The pill bottles handed to the clinical coordinator will be identical for placebo and CC.

Study Type: Interventional

Study Design: Randomized Treatment assignment

Intervention Model: Parallel Assignment

Masking: Double Blind (Subject, Investigators, coordinators, nurses)

Primary Purpose: Treatment

Intervention:

1) Curcumin (turmeric extract), over the counter supplement (1 capsule/three times a day).

Producer Company: Oregon Wild Harvest

The dosage used for the patients is based on the amount recommended by the producer Company (and approved by FDA). According to the Company, each capsule contains: 270 mg of pure curcuminoids (curcumin) and 3 mg of black pepper extract. Recommended serving size is 3

Title: Clinical Action of Curcumin/Turmeric In chronic Subdural hematoma recurrence (CACTIS)

capsules per day. In total, the patients will receive **810 mg** of pure curcumin and **9 mg** of black pepper extract (pepperine/BioPerine) per day.

The active Curcumin/Bioperine capsules will be over encapsulated with the orange size 00 vegetarian capsules so that they cannot be distinguished from the placebo capsules.

2) Placebo (1 capsule/three times a day).

Producer: Investigational Drug Services

IDS will prepare the placebo capsules by placing the cellulose directly into the orange size 00 vegetarian capsules so they are indistinguishable from the curcumin/bioperine pills.

• Inclusion and Exclusion Criteria

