cSDH patients will take one capsule three times a day for up to 60 days. Because maximum treatment duration is 60 days, IDS will dispense a total of 180 capsules. IDS will dispense this amount on two occasions to reduce waste and save cost for cases in which treatment may end early. They will undergo standard post-operative care in regard to imaging and clinical follow-up.

- Patients will begin taking placebo or CC within 24 hours post-operatively and able to take oral medication. It will then be continued TID.
- CT Imaging:
 - Pre-operative CT SOC scan
 - If the hematoma volume is < 115 cc, the patient will not be included in the study
 - Post-operative day one CT SOC scan within 24 hours of surgery.
 - Post subdural drain removal SOC scan usually 1-2 days after surgery.

Title: Clinical Action of Curcumin/Turmeric In chronic Subdural hematoma recurrence (CACTIS)

- If the residual total hematoma cavity volume is $<80\text{cc}$, the patient will be dropped from study, as the curcumin has not had time to influence the patient's reabsorption.
- *During the SOC one week follow-up appointment without a CT scan*, the attending will decide on the need for a repeat CT scan in 4 weeks based on the patient's **post-subdural drain removal SOC scan**.
 - If the residual total hematoma cavity volume is $\geq 80\text{cc}$, the patient will receive an additional CT scan (SOC) for an appointment one month following the previous appointment (Approximately post-operative day 37)
 - If there is a decline in neurological exam or other clinical concern, the neurosurgeon may perform an earlier CT scan
- This will continue on a monthly basis for 6 months, or until residual total hematoma cavity volume is $< 80\text{cc}$
 - **Resolution** will be defined as residual total hematoma cavity volume $< 80\text{cc}$
 - Patients with resolution of their hemorrhage will no longer require Tx or follow-up visits. Their pills will be returned and discarded. These patients will receive phone **call** follow-ups at 1-month, 6-month, and 18-month intervals

All radiographic imaging discussed here is our institution's standard of care for the management of SDH. If Tx discontinued, the patients will still be followed according to the schedule below

- Study Follow-Up **Phone Calls**
 - 1 month, 6 months, 18 months
 - Modified Ranking Scale (MRS) (Appendix 3)
 - Markwalder Grading Scale (Appendix 4)

5. Study Endpoints

5.1. Describe the primary and secondary study endpoints.

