- 5.1.1. Primary: Change, rate of change, and time-to-resolution in total hematoma volume of cSDH compared to post-subdural drain scan of less than 80cc in post-surgical patients
- 5.1.2. Secondary: Recurrence rate of cSDH
- 5.1.3. Secondary: Markwalder and mRS progression.
- 5.1.4. Secondary: Rate of surgical intervention in CC and placebo groups.
- 5.1.5. Secondary: Rate of persistent or recurrent neurological symptoms in CC and placebo groups.

5.2. Safety Endpoints:

- 5.2.1. To assess the tolerability of CC in patients via frequency of any side effects, or adverse events as defined by the National Institute of Health's Common Terminology Criteria for Adverse Events (NCI-CTCAE, Version 4.0)
- 5.2.2. Subject participation will be terminated if any reported adverse events, discomfort, or distress is detected.

6. Research Setting

This is a single center study that will take place at the University of New Mexico Hospital. New patients admitted directly to the UNM Neurosciences Intensive Care Unit (NSICU) as a transfer from

Title: Clinical Action of Curcumin/Turmeric In chronic Subdural hematoma recurrence (CACTIS)

an outside hospital as well as patients admitted directly through the UNM Emergency Department (ED), with subdural hematomas will be identified and recruited as potential subjects. All surgical operations will take place in the main operating room (OR) at UNMH. The perioperative care of the enrolled patients, as well as the non-surgically managed patients will take place both in the NSICU as well as the Neurosurgical step-down unit.

Once patients have been discharged from the hospital, all follow-up appointments will take place in the Clinical Neurosciences Center located adjacent to UNMH. Patients will follow-up in the subdural clinic, staffed by **[name]**, Principal Investigator.

7. Resources Available

[name] is the chairman of the Department of Neurosurgery. He has been a part of the UNM faculty since 2005, and has significant experience with both the surgical/medical management of patients with subdural hematomas, as well as with oversight on research projects. [name] is personally responsible for the development of the 24-bed Neurosciences ICU where neurosurgical patients are cared for, as well as the multidisciplinary Neurosciences center where patients are followed in an outpatient setting. **He will see all patients enrolled in the trial in his clinic.**

[name] has participated in two clinical trials.

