 - Patients who are no longer in the study will be **called** at 1 month, 6 months, and 18 month intervals

Table 1. CT Scan Variables on cSDH Characteristics and Quantitation

CT SCAN MEASUREMENTS			
Pre-operative: Scan #1			
Location of SDH (Left/Right)	CT Density (HU)	Midline shift at 3 rd ventricle (mm)	Volume (cc)
Post-operative: POD#1 Scan			
Subdural Fluid Volume (cc)	Pneumocephalus Volume (cc)	Total Residual Cavity Volume (cc)	Midline shift at 3 rd ventricle (mm)
Post-operative: Post-SDD removal Scan			
Subdural Fluid Volume (cc)	Pneumocephalus Volume (cc)	Total Residual Cavity Volume (cc)	Midline shift at 3 rd ventricle (mm)
Post-operative: one week (staple removal)			
Subdural Fluid Volume (cc)	Pneumocephalus Volume (cc)	Total Residual Cavity Volume (cc)	Midline shift at 3 rd ventricle (mm)
Post-operative: 4 weeks			
Subdural Fluid Volume (cc)	Pneumocephalus Volume (cc)	Total Residual Cavity Volume (cc)	Midline shift at 3 rd ventricle (mm)

Clinic Follow-up (Subdural clinic):

1. A subdural clinic has been established to see all subdural patients. [name] will evaluate ALL patients in the trial during their appointments. A research team member will also be present to help coordinate data collection, tracking of pills, measurements, and follow-up.
2. Patients will be seen **1 week** post-operatively for staple removal.
 - a. Subdural volumetric measurements of remaining subdural fluid from last scan will be completed.
 - i. Patients with a residual total hematoma cavity volume $< 80\text{cc}$ will be instructed to discontinue the pills. Unused medication will be retrieved from the subjects and returned to IDS for destruction. They will not have additional neurosurgical imaging or follow-up required, unless deemed necessary by the neurosurgery attending.

Title: Clinical Action of Curcumin/Turmeric In chronic Subdural hematoma recurrence (CACTIS)

1. They will continue to be followed by the study team with a 6 month and 18-month phone call

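### Resolution is judged on a cavity volume that includes post-operative air; adjust for baseline air and add a supporting fluid-volume analysis

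*Combined protocol and SAP*

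**What the plan says.** - **Objective 1 and the central hypothesis** name total hematoma cavity volume over six months, relative to the post-drain scan, as the target.
- **Section 2, CT Scans**, describes the recurrence predictor in the cited imaging study as a residual cavity total, "fluid and pneumocephalus) based on post-subdural drain removal CT scan". It then adopts that study's thresholds: "our protocol will only include patients with a pre-operative hematoma volume of" at least 115cc, with a volume below 80cc as the working definition of resolution.
- **Section 4, Study Timelines**, and **Study Procedures**: resolution "will be defined as residual total hematoma cavity volume" below 80cc. If the same volume is already below 80cc on the post-drain scan, "the patient will be dropped from study, as the curcumin has not had time to influence" reabsorption. The post-drain scan is usually 1-2 days after surgery, and the next scheduled scan is at about day 37.
- **Table 1** gives each listed post-operative scan a subdural fluid field, a field "Pneumocephalus Volume (cc" and a field "Total Residual Cavity Volume (cc".
- **Section 5.1.1** words the primary endpoint as "Change, rate of change, and time-to-resolution in total hematoma volume of cSDH", without the word cavity.
- **Data Analysis, Statistical analysis**, plans linear mixed models for hematoma volume and survival analysis for time to resolution. It does not say whether the volume is fluid or total, and it names no analysis that uses the fluid or air fields.

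**The concern.** The baseline volume is measured soon after surgery, when the cavity can hold air. The mechanism set out at the end of Section 2 is reduced vessel leakage and less accumulation of blood; no effect on air is claimed. Part of the measured volume is therefore something the treatment is not expected to act on.

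Two things are at stake. First, a resolution event can occur with no change in fluid, and such events would fall on both arms alike. The protocol already accepts the principle: it removes patients below 80cc at the post-drain scan because treatment has had no time to work. An event produced by air loss is no more a treatment effect, yet it would count. Second, reaching 80cc ends both the capsules and the scheduled scans, so such an event also closes the patient's volume series.

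**Working it through.** **1. Is air part of the volume?** The bracketed definition in Section 2 describes the cited study. The trial adopts that study's 80cc threshold and uses the same cavity term in its own resolution rule. Table 1 then lists fluid, pneumocephalus and total residual cavity side by side. Read together, the trial's total includes air.

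**2. Who is affected?** Let F be fluid and A air at the post-drain scan. A patient is retained if F + A ≥ 80. If the air later goes and fluid is unchanged, the total becomes F. So crossing by air loss alone requires F < 80 ≤ F + A.
- Example: 65 + 25 = 90, retained; later 65 + 0 = 65, resolved.
- A patient with F ≥ 80 must still lose fluid to cross.
- If fluid fills the space instead (65 + 25 becoming 90 + 0), the total does not fall and there is no event. The documents do not say which happens.

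The group at risk can therefore be counted from the baseline fields in Table 1.

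**3. Time to resolution.** The plan's only related figure is that 25 per group will not reach 80% power unless resolution is 50% greater on curcumin. It cannot be reproduced uniquely, because the placebo rate, alpha and test are not given. With two-sided alpha 0.05 and a pooled test of two proportions:
- read as 50 absolute points, power is 0.97 to 0.99 for placebo rates of 5% to 45%;
- read as a relative 50%, power runs from 0.13 (20% vs 30%) to 0.86 (65% vs 97.5%).

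For illustration I take true rates of 30% vs 70%, where Section 4's 24 per arm gives power of 0.81. Suppose a share f of each arm crosses by air loss alone, independently of fluid. The observed rate becomes p' = f + (1 − f)p, and the difference shrinks by the factor (1 − f). The share f is an assumption; nothing in the documents fixes it.

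| f | Placebo | Curcumin | Difference (points) | Power |
|---|---|---|---|---|
| 0 | 30% | 70% | 40 | 0.81 |
| 0.1 | 37% | 73% | 36 | 0.72 |
| 0.2 | 44% | 76% | 32 | 0.63 |
| 0.3 | 51% | 79% | 28 | 0.53 |
| 0.4 | 58% | 82% | 24 | 0.44 |

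This treats resolution as a yes/no outcome, a simple stand-in for the survival analysis. Using 25 per group changes little (0.83 at f = 0).

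**4. Change and rate of change.** The change in total is the change in F plus the change in A. If assignment is unrelated to baseline air and air is lost equally in both arms, the air term cancels from the expected difference and only adds variance. With r = SD of air / SD of fluid, the SD grows by √(1 + r²). For an illustrative fluid effect of 0.8 SD with 24 per arm, power is 0.79 at r = 0, 0.77 at r = 0.25, 0.70 at r = 0.5 and 0.50 at r = 1.

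The 95% range for chance imbalance in mean baseline air is ±1.96 × SD × √(2/24). For assumed air SDs of 5, 10 and 15cc this is ±2.8, ±5.7 and ±8.5cc.

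**The case against.** The strongest reply is that cavity volume is the declared target. Objective 1 and the hypothesis name it, and the 80cc threshold comes from a study that used the fluid-plus-air total as its predictor. In a pilot with an openly provisional definition, using it is not an error. That stands, and it is why the endpoint and the visit rule should not change.

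Three further points also stand:
- No air volume, absorption rate or count of affected patients appears anywhere in the documents, so no size can be attached.
- Chance imbalance in air is ordinary sampling error, which a confidence interval already reflects.
- The fluid and air rows of Table 1 stop at 4 weeks, and the clinic visits near days 37 and 67 list subdural thickness measurements. A six-month fluid analysis is therefore not simply a matter of using data already on the form.

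None of this answers the remaining gap. Baseline air is already a field on the post-drain scan, it is a plausible source of variation unrelated to treatment, and the analysis does not use it. The volume terms also differ between Objective 1, Section 5.1.1 and the Statistical analysis text.

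**Conclusion.** The point holds as a modest, inexpensive improvement. Cavity volume including air governs both retention at the post-drain scan and resolution, so resolution can be reached with fluid unchanged. This can dilute time to resolution. For change and rate of change, the direct effect of air is noise and possible chance imbalance.

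A reader might infer more, and the documents do not support it:
- **That some patients will cross by air loss alone, or what percentage.** No air volumes are given. Spreading post-drain volumes over an assumed range such as 80-140cc has no source: 140 ml is the pre-operative stratification cut. Such a percentage would also count patients who would have resolved through fluid loss anyway.
- **That all three primary measures are diluted.** Equal air loss cancels from the mean difference in volume.
- **That one arm is favoured.** Air unrelated to assignment costs sensitivity; it does not create a systematic advantage.
- **That curcumin has been shown not to affect air.** This is a reasonable inference from the stated mechanism, not a statement in the protocol.

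The powers above rest on assumed values of f, r and the true rates. They show direction and scale, not an estimate for this trial.

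**What to change.** Keep total hematoma cavity volume as the primary measure and leave the existing 80cc visit rule as it is. In the Statistical analysis text:

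1. Add pneumocephalus volume from the post-drain scan as a covariate in the cavity-volume mixed model and in the time-to-resolution model.
2. Prespecify the same mixed model on subdural fluid volume as a supporting analysis.
3. Report, by arm, how many patients have total ≥ 80cc but fluid < 80cc at the post-drain scan. The covariate cannot undo events already produced by air loss; this count shows how much dilution is possible and informs the definition for a larger trial.
4. Use *total hematoma cavity volume* in Section 5.1.1 and in the Statistical analysis text.

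The cost is one more model to report and one more covariate in a trial of 48. The Table 1 fluid and air fields must also be carried forward to the later monthly scans. Those scans are already performed, so no additional imaging, visits or patients are needed.
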